**6.7.5 Other Efficacy Parameters (Immune Response Criteria)**

**6.7.5.1 Evaluation of Response by irRECIST**

Secondary objectives of this study involve assessment of ORR and PFS based in immune response criteria as outlined below (see Guidelines for the evaluation of immune therapy activity in solid tumors: immune-related response criteria. Wolchok JD et al. Clin Cancer Res 2009;15(23):7412-20, Nishino et al. Clin Cancer Res 19(14):3936-43, and Bohnsack O. et al., *Adaptation of the immune related response criteria: irRECIST*. Annals of Oncology (2014) 25 (suppl\_4): iv361-iv372. 10.1093/annonc/mdu342, 2014).

irRECIST criteria are based on irRC criteria (Wolchok et al) adapted for unidimensional measurement as outlined by Nishino et al. The adaptation described by Bohnsack et al. further aligns irRECIST to allow for assessment of

baseline non-target lesions and new non-measurable lesions and discusses the impact of those lesions on the overall tumor response assessment. The adaptation by Bohnsack et al. allows for evaluation of subjects with non-target disease only and subjects in the adjuvant setting (not applicable for this study in subjects with metastatic disease).

Overall response using the irRECIST is based on tumor burden as follows:

irCR	Complete disappearance of all lesions (whether measurable or not, and no new lesions) Lymph nodes must decrease to < 10 mm in short axis. Confirmation of response is not mandatory.
irPR	Decrease in tumor burden $\geq 30\%$ in TMTB relative to baseline confirmed by a consecutive assessment at least 4 weeks after first documentation, non-target lesions are irNN, and no equivocal progression of new non-measurable lesions.
irSD	Not meeting criteria for irCR, irPR, in absence of irPD
irPD	Increase in tumor burden $\geq 20\%$ increase and minimum 5 mm absolute increase in TMTB compared to nadir, or irPD for non-target or new non-measurable lesions confirmed by a repeat, consecutive assessment no less than 4 weeks from the date first documented
irNN	No target disease was identified at baseline and at follow-up the subject fails to meet criteria for irCR or irPD.

irNN = irNon-CR/Non-PD

TMTB = Total measurable tumor burden

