### 2.4.2 Secondary Endpoints

**2.4.2.1** The best overall responses for both RECIST 1.1 and irRECIST are defined as the best response achieved across all time points prior to progression (for example, a subject who has SD at first assessment, PR at second assessment, and PD on last assessment has a best overall response of PR). Please Note: In the case of SD, measurements must have met the SD criteria at least once after study entry at a minimum interval of 12 weeks from initiation of treatment.

**2.4.2.2** The immune-related response rate is defined as the percentage of subjects with unresectable refractory *KRAS/NRAS/BRAF* wild-type MSS mCRC who achieve a CR+PR by 12 weeks to panitumumab/nivolumab/ipilimumab or panitumumab/nivolumab therapy per irRECIST criteria. (See section 6.7.5.1)

**2.4.2.3** Assessment of immune-related PFS is defined as starting from the first day of treatment or Day 1 (D1) until the event of disease progression as defined by irRECIST, or death from any cause in subjects with unresectable refractory *KRAS/NRAS/BRAF* wild-type MSS mCRC (See section 6.7.5.1). Any subject that has not had a documented event at the time of analysis will be censored. Assessment of PFS (as defined by RECIST 1.1) is defined from D1 of treatment until the event of disease progression occurs or death from any cause in subjects with unresectable refractory *KRAS/NRAS/BRAF* wild-type MSS mCRC. Any

October 01,,  
2020

subject that has not had a documented event at the time of analysis will be censored.

- 2.4.2.4 OS is defined as the time from D1 of treatment until death from any cause. Any subject that has not died by the analysis date will be censored.
- 2.4.2.5 The duration of response as defined by RECIST 1.1 will be defined as the time elapsed from first scan documenting partial response or complete response until the event of disease progression occurs. Any subject that has not had a documented progression at the time of analysis will be censored. The duration of response as defined by irRECIST will be defined as the time elapsed from first scan documenting partial response or complete response until the event of disease progression occurs. Any subject that has not had a documented progression at the time of analysis will be censored.
- 2.4.2.6 Treatment-related adverse events will be assessed per NCI-CTCAE v4.03.

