### **3.0 SUBJECT ELIGIBILITY**

#### **3.1 Inclusion Criteria**

Subjects must meet all of the inclusion criteria as listed below to participate in this study.

- 3.1.1 Histologically or cytologically confirmed colorectal adenocarcinoma, with unresectable metastatic or locally advanced disease documented on diagnostic imaging studies.
- 3.1.2 Previously received 1-2 prior lines of therapy. Subjects who relapse within 6 months of adjuvant chemotherapy comprised of oxaliplatin and a fluoropyrimidine will have their adjuvant therapy count as one prior line of therapy.
- 3.1.3 Confirmed wild-type in KRAS and NRAS codons 12, 13, 59, 61, 117, and 146; and BRAF codon 600, by standard of care testing of tumor specimen. Tissue used for testing may have been collected from primary or metastatic site.
- 3.1.4 Microsatellite stable as detected by PCR-based assay OR CLIA-certified sequencing methodology such as Foundation One; OR mismatch repair proficient as detected by immunohistochemistry showing intact nuclear staining of MLH1, MSH2, MSH6, and PMS2.
- 3.1.5 Radiographically measurable disease present per RECIST 1.1

- 3.1.6** Age  $\geq$  18 years at the time of consent.
- 3.1.7** Eastern Cooperative Oncology Group (ECOG) performance status 0 or 1.
- 3.1.8** Blood counts performed within 3 weeks prior to starting study therapy must have absolute neutrophil count  $\geq$  1,500/mm^3, platelets  $\geq$  100,000/mm^3, and hemoglobin  $\geq$  9 g/dL.

**\*Note:** Hematology and other lab parameters that are  $\leq$  grade 2 BUT still meet criteria for study entry are allowed. Furthermore, changes in laboratory parameters during the study should not be considered adverse events unless they meet criteria for dose modification(s) of study medication outlined by the protocol and/or worsen from baseline during therapy.

- 3.1.9** Liver function tests performed within 3 weeks prior to starting study therapy must have total bilirubin  $\leq$  1.5 x upper limit of normal (ULN), alanine aminotransferase and aspartate aminotransferase  $\leq$  3 x ULN, and albumin  $\geq$  2.5 g/dL.
- 3.1.10** Serum creatinine performed within 3 weeks prior to starting study therapy must be  $\leq$  1.5 x ULN, or have calculated creatinine clearance (using Cockcroft-Gault formula provided in Appendix 11.3) of  $\geq$  50 mL/minute.

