### **6.7.2 Baseline Documentation of Target and Non-Target Lesions**

All measurable lesions up to a maximum of 5 lesions total (and a maximum of two lesions per organ) representative of all involved organs should be identified as target lesions and will be recorded and measured at baseline.

Target lesions should be selected on the basis of their size (lesions with the longer diameter), be representative of all involved organs, but in addition should be those that lend themselves to reproducible repeated measurements.

A sum of the diameters (longest for non-nodal lesions, short axis for nodal lesions) for all target lesions will be calculated and reported as the baseline sum diameters. If lymph nodes are to be included in the sum, only the short axis is added into the sum. The baseline sum diameters will be used as reference to further characterize the objective tumor response of the measurable dimension of the disease.

All other lesions (or sites of disease) including pathological lymph nodes should be identified as non-target lesions and should also be recorded at baseline. Measurements are not required, and these lesions should be followed as “present” or “absent”, or in rare cases “unequivocal progression”.

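### Section 6.7.5.1 uses irNN in two conflicting senses, and on either one a partial responder whose non-target lesions have all cleared is scored irSD rather than irPR

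*Combined protocol and SAP*

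**What the plan says.** The irRECIST table in Section 6.7.5.1 sets these rules:

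- irPR needs a TMTB fall of at least 30% from baseline, confirmed at least 4 weeks later, and "non-target lesions are irNN, and no equivocal progression of new non-measurable lesions".
- The irNN row reads "No target disease was identified at baseline and at follow-up the subject fails to meet criteria for irCR or irPD". This describes a subject, not a lesion.
- The line below the table reads "irNN = irNon-CR/Non-PD", with no condition on target disease.
- irCR is "Complete disappearance of all lesions (whether measurable or not, and no new lesions".
- irSD is the residual category: "Not meeting criteria for irCR, irPR, in absence of irPD".

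On the population, inclusion criterion 3.1.5 requires "Radiographically measurable disease present per RECIST 1.1". Section 6.7.2 says that measurable lesions, up to the stated maximum and "representative of all involved organs should be identified as target lesions and will be recorded and measured at baseline".

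Section 2.4.2.2 counts subjects with "CR+PR by 12 weeks to panitumumab/nivolumab/ipilimumab or panitumumab/nivolumab therapy per irRECIST criteria". Best response (2.4.2.1) and duration of response (2.4.2.5) are also reported by irRECIST.

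**The concern.** The irPR row depends on a term that the same table reserves for subjects this trial cannot enrol. The expansion under the table offers a workable meaning, but the section does not say which meaning governs. Even the workable meaning demands that non-target disease be neither gone nor progressing, so complete clearance of non-target lesions fails the condition.

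Three secondary endpoints rest on this row: the 12-week irRECIST response rate, irRECIST best response and irRECIST duration of response. A subject sent to irSD leaves the numerator of the first two. With no documented irPR or irCR, that subject also has no start date for the third. Section 6.7.3 defines RECIST 1.1 partial response in the target lesions with no requirement that non-target disease persist. The same scans could therefore give PR on one set of criteria and irSD on the other because of wording. In a multicenter trial, readers could also code identical scans differently.

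**Working it through.** **The plan's own figure.** The documents give no figure for irRECIST response. The nearest is the Simon design in Section 8.2 for the RECIST 1.1 endpoint: 32 subjects, then 56; suspend at 6 or fewer responders; positive at 17 or more. The probability of a positive result is Σ over x = 7 to 32 of P(X₁ = x) × P(X₂ ≥ 17 − x), with X₁ ~ Bin(32, p) and X₂ ~ Bin(24, p).

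- p = 0.22: 0.0903 (plan: α = 0.10)
- p = 0.35: 0.8012 (plan: power 80%)

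A minimax search returns the same design. It reproduces, and nothing in it uses the irPR row.

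**Row sense of irNN.** Every eligible subject has measurable disease (3.1.5), and measurable lesions become target lesions (6.7.2). irPR itself needs a fall in measurable burden from baseline. A subject with no target disease at baseline therefore cannot occur here, and no subject with non-target lesions can satisfy irPR.

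**Expansion sense of irNN.** Take non-CR/non-PD as the status of the non-target lesions. Section 6.7.4 gives disappearance of non-target lesions a separate status, CR. Lesions that have gone are therefore not irNN.

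**Classification.** Consider a confirmed TMTB fall of at least 30%, targets still visible, nothing progressing and no new lesions:

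| Non-target lesions | Row sense | Expansion sense | Condition restated as no non-target progression |
|---|---|---|---|
| Persisting, not progressing | irSD | irPR | irPR |
| All disappeared | irSD | irSD | irPR |
| None at baseline | irSD, or irPR if an empty condition counts as met | irSD, or irPR if an empty condition counts as met | irPR |

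The cases reaching irPR are 0 of 3 on the row sense (1 of 3 if an empty condition counts as met), 1 of 3 on the expansion sense (2 of 3 likewise), and 3 of 3 once restated. The middle line is irSD on every reading of the current text: it is not irCR because targets remain, not irPR because the non-target lesions are CR, and not irPD.

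**Size.** Each subject moved lowers the rate by 1/56 = 1.8 percentage points. As an illustration only, assume 20 of 56 subjects are irRECIST responders under the restated rule (20/56 = 35.7%; 0.35 × 56 = 19.6) and a share f of them is moved to irSD. The reported rate is 20(1 − f)/56:

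| f | Reported |
|---|---|
| 10% | 18/56 = 32.1% |
| 20% | 16/56 = 28.6% |
| 30% | 14/56 = 25.0% |
| 40% | 12/56 = 21.4% |

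Both the 20 and the range of f are assumptions. Only partial responders can be moved by the non-target-clearance gap.

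**The case against.** **The expansion is the document's own.** A reader might infer from the irNN row that nobody can be irPR and that the irRECIST response rate reduces to the irCR rate. The documents do not support this. The line under the table expands irNN as non-CR/non-PD, and the irPR row applies it to lesions. This part of the objection stands: the text has two conflicting definitions, not one impossible criterion.

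**No non-target lesions at baseline.** A reader might infer that these subjects are also certainly misclassified. A condition on non-target lesions may fairly be taken as met when there are none. This also stands: the case is ambiguous.

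**Tumor markers.** Section 6.7.4 requires marker normalization for non-target CR under RECIST 1.1. If that carries over, a subject whose non-target lesions vanish while the marker stays raised would still be non-CR/non-PD, and so eligible for irPR. This would narrow the gap without closing it, and the irRECIST table does not mention markers.

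**Cited publications.** The section refers to published criteria, which readers might follow instead. What those say cannot be judged from the documents. The protocol applies the criteria as it outlines them, and that outline is where the conflict lies.

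**Other reasons for a lower rate.** irPR needs confirmation at least 4 weeks later, and the RECIST 1.1 PR definition in 6.7.3 states no such interval. A lower irRECIST rate would therefore not by itself prove this fault.

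**Limited consequence.** These endpoints are secondary, estimated with confidence intervals, and have no hypothesis test or decision rule. That limits the severity but does not make the category right.

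**Conclusion.** The concern holds in this limited form. Section 6.7.5.1 does not settle what irNN means, and on either meaning target partial response with complete non-target clearance is scored irSD. On the expansion sense, a better non-target outcome gives a worse category.

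If the table is applied as written, the 12-week irRECIST response rate and irRECIST best response are biased downward, and the affected responders are missing from irRECIST duration of response. This concerns subjects not otherwise credited with irPR or irCR; complete responders are untouched, because the irCR row does not use irNN.

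The size is unknown. It depends on how many partial responders clear all non-target disease, which the documents do not indicate. A reader might apply an assumed loss to the 17 of 56 in Section 8.2, but that is the RECIST 1.1 decision threshold, not a forecast of irRECIST responders, and it may include complete responders.

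The irPR row's reference to equivocal progression of new lesions, where Section 6.7.4 uses unequivocal, may be a slip. It is worth checking but carries no weight here.

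The primary endpoint, the sample size and the two-stage rule do not change.

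**What to change.** Revise the table in Section 6.7.5.1:

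1. State the irPR non-target condition as no non-target progression: non-target lesions in CR, non-CR/non-PD, or none at baseline.
2. Use a separate, lesion-level term for non-CR/non-PD.
3. Keep the category for subjects without target disease out of the irPR condition.
4. Say whether the marker requirement of Section 6.7.4 applies to non-target CR under irRECIST.
5. Check whether equivocal should read unequivocal in the irPR row.

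Then re-derive all irRECIST calls from the recorded lesion data. Section 6.7.2 already has target lesions measured and non-target lesions followed as present or absent, so no new scans are needed. The cost is a wording amendment and a re-run of the irRECIST derivation.

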## 7.0 ADVERSE EVENTS

### 7.1 Definitions

#### 7.1.1 Adverse Event (AE)

An adverse event (AE) is any untoward medical occurrence (e.g., an abnormal laboratory finding, symptom, or disease temporally associated with the use of a drug) in a subject or clinical investigation subject administered a pharmaceutical product and which does not necessarily have a causal relationship with this treatment. An AE can therefore be any unfavorable and unintended sign (including an abnormal laboratory finding), symptom, or disease temporally associated with the use of a medicinal product, whether or not related to the medicinal product.

Hospitalization for elective surgery or routine clinical procedures that are not the result of an AE (e.g., surgical insertion of central line) need not be considered AEs and should not be recorded as an AE. Disease progression should not be recorded as an AE unless it is attributable by the investigator to the study therapy.

### 7.1.2 Suspected Adverse Reaction (SAR)

A suspected adverse reaction (SAR) is any AE for which there is a *reasonable possibility* that the drug is the cause. *Reasonable possibility* means that there is evidence to suggest a causal relationship between the drug and the AE. A suspected adverse reaction implies a lesser degree of certainty about causality than adverse reaction, which means any adverse event caused by a drug.

Causality assessment to a study drug is a medical judgment made in consideration of the following factors: temporal relationship of the AE to study drug exposure, known mechanism of action or side effect profile of study treatment, other recent or concomitant drug exposures, normal clinical course of the disease under investigation, and any other underlying or concurrent medical conditions. Other factors to consider in considering drug as the cause of the AE:

- Single occurrence of an uncommon event known to be strongly associated with drug exposure (e.g., angioedema, hepatic injury, Stevens-Johnson Syndrome)
- One or more occurrences of an event not commonly associated with drug exposure, but otherwise uncommon in the population (e.g., tendon rupture); often more than once occurrence from one or multiple studies would be needed before the sponsor could determine that there is *reasonable possibility* that the drug caused the event.
- An aggregate analysis of specific events observed in a clinical trial that indicates the events occur more frequently in the drug treatment group than in a concurrent or historical control group

### 7.1.3 Unexpected AE or SAR

An AE or SAR is considered unexpected if the specificity or severity of it is not consistent with the applicable product information (e.g., Investigator's Brochure (IB) for an unapproved investigational product or package insert/summary of product characteristics for an approved product). Unexpected also refers to AEs or SARs that are mentioned in the IB as occurring with a class of drugs or as anticipated from the pharmacological properties of the drug but are not specifically mentioned as occurring with the particular drug under investigation.

### 7.1.4 Serious AE or SAR

An AE or SAR is considered serious if, in the view of either the investigator or sponsor, it results in any of the following outcomes:

- Death;
- Is life-threatening (places the subject at immediate risk of death from the event as it occurred);

- Requires in subject hospitalization (>24 hours) or prolongation of existing hospitalization;\*
- Results in congenital anomaly/birth defect;
- Results in a persistent or significant incapacity or substantial disruption of the ability to conduct normal life functions;
- Important medical events that may not result in death, be life-threatening, or require hospitalization may be considered a serious adverse drug experience when, based upon appropriate medical judgment, they may jeopardize the subject or subject and may require medical or surgical intervention to prevent one of the outcomes listed in the definition. For reporting purposes, also consider the occurrences of pregnancy as an event which must be reported as an important medical event.
- Potential drug induced liver injury (DILI) is also considered an important medical event.
- Suspected transmission of an infectious agent (eg, pathogenic or nonpathogenic) via the study drug is an SAE.
- Although pregnancy, overdose, and cancer are not always serious by regulatory definition, these events must be handled as SAEs.

\*Hospitalization for anticipated or protocol specified procedures such as administration of chemotherapy, central line insertion, metastasis interventional therapy, resection of primary tumor, or elective surgery, will not be considered serious adverse events.

Pregnancy that occurs during the study must also be reported as an SAE.

## **7.2 Documentation of non-serious AEs or SARs**

For non-serious AEs or SARs, documentation must begin from day 1 of study treatment and continue through the 100-day follow-up period after treatment is discontinued.

Collected information should be recorded in the electronic Case Report Forms (eCRF) for that subject. Please include a description of the event, its severity or toxicity grade, onset and resolved dates (if applicable), and the relationship to the study drug. Documentation should occur at least monthly.

## **7.3 SAEs or Serious SARs**

### **7.3.1 Timing**

After informed consent but prior to initiation of study medications, only SAEs caused by a protocol-mandated intervention will be collected (e.g. SAEs related to invasive procedures such as biopsies, medication washout).

For any other experience or condition that meets the definition of an SAE or a serious SAR, recording of the event must begin from day 1 of study treatment and continue through the 100-day follow-up period after treatment is discontinued.

### 7.3.2 Documentation and Notification

SAEs or Serious SARs must be recorded in the SAE console within Oncore™ for that subject within 24 hours of learning of its occurrence. Additionally, the Regulatory Associate and Medical Monitor must also be notified via email of all SAEs within 24 hours of learning of its occurrence.

### 7.3.3 Reporting

#### IRB Reporting Requirements:

##### UNC:

- The UNC-IRB will be notified of all SAEs that qualify as an Unanticipated Problem as per the UNC IRB Policies using the IRB's web-based reporting system within 7 days of the Investigator becoming aware of the problem. These events must be reported to the sponsor within 24 hours of learning of the occurrence.

##### Affiliate sites:

- For affiliate sites using a local IRB of record, please submit adverse events per local IRB policy.
- For affiliate sites relying on the UNC-IRB, an aggregated list of all SAEs will be submitted to the UNC IRB annually at the time of study renewal according to the UNC IRB policies and procedures. In addition, any SAEs that qualify as an Unanticipated Problem will be entered into Oncore by the affiliate site and reported to the UNC IRB by the Multicenter Regulatory Associate using the IRB's web-based reporting system within 7 days of the Investigator becoming aware of the problem.

